11.7. Biomarker Analyses

Biomarker studies are designed to identify markers predictive of response (or resistance) to daratumumab. Analyses will be performed and stratified by clinical covariates or molecular subgroups using the appropriate statistical methods (eg, parametric or non-parametric, univariate or multivariate, analysis of variance, or survival analysis, depending on the endpoint). Correlation of baseline expression levels or changes in expression levels with response or time-to-event endpoints will identify responsive (or resistant) subgroups in addition to genes and pathways attenuated following treatment with daratumumab. In order to remove any confounding influence of prognostic factors, any predictive biomarker identified in this study could be verified in a prospective clinical study with a control treatment arm.

Any biomarker measures will be listed, tabulated, and where appropriate, plotted. Subjects will be grouped by prescribed dose. Complete responders will be utilized to investigate the prognostic effect of MRD on PFS. MRD analysis will include evaluation of data from other studies to determine if decreased MRD is seen with daratumumab + Rd based chemotherapy regimen compared with the Rd based chemotherapy alone.

Results of biomarker and pharmacodynamic analyses may be presented in a separate report. Planned analyses are based on the availability of clinically valid assays and may be deferred if emerging study data show no likelihood of providing useful scientific information.

In addition, due to the small sample sizes of high-risk subgroups within the multiple myeloma subject population, a meta-analyses may be performed across daratumumab Phase 3 studies to evaluate clinical efficacy of daratumumab with standard of care agents in pre-specified subgroups of multiple myeloma subjects. The meta-analysis protocol will pre-specify the objective of the meta-analysis, the criteria for inclusion and exclusion of studies, the hypotheses and endpoints, and statistical methods including a method for investigation of heterogeneity. This meta-analytic approach, supported by high-quality data from the individual studies, should be able to provide definitive evidence on the effectiveness of daratumumab in the subpopulation of multiple myeloma subjects with high-risk molecular abnormalities. In a similar fashion, a meta-analysis examining

MRD negativity in daratumumab treated subjects in frontline, newly diagnosed multiple myeloma (MMY3006, MMY3007, MMY3008) may also be performed.

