3. STUDY DESIGN AND RATIONALE

3.1. Overview of Study Design

This is a randomized, open-label, active controlled, parallel-group, multicenter study in subjects at least 18 years of age with newly diagnosed multiple myeloma who are not candidates for high dose chemotherapy and ASCT. Approximately 730 subjects will be enrolled in this study with 365 subjects planned per treatment arm.

A diagram of the study design is provided in Figure 2.

Figure 2: Schematic Overview of the Study

NOTE: After Study MMY3008 transitions to long-term survival follow-up, an end-of-treatment visit is no longer required.

Subject participation will include a Screening Phase, a Treatment Phase, and a Follow-up Phase. The Screening Phase will be up to 21 days before Cycle 1, Day 1. The Treatment Phase will extend from Day 1 of Cycle 1 until discontinuation of all study treatment. For subjects assigned to DRd, daratumumab will be administered weekly for the first 8 weeks (Cycles 1-2) of treatment and then every other week for 16 weeks (Cycles 3-6), then every 4 weeks (from Cycle 7 and beyond) until disease progression or unacceptable toxicity. This will equate to 9 consecutive weeks of dosing at the start of the study and a total of 23 doses in the first year. Lenalidomide will be administered at a dose of 25 mg orally (PO) on Days 1 through 21 of each 28-day cycle, and dexamethasone will be administered at a dose of 40 mg once a week in both treatment arms. Subjects in both treatment

arms will continue lenalidomide and dexamethasone until disease progression or unacceptable toxicity. In the DRd arm, subjects will continue on daratumumab until disease progression or unacceptable toxicity. Randomization will be stratified by International Staging System (I vs II vs III), region (North America vs Other), and age (<75 vs ≥75), using an equal allocation ratio of 1:1.

Measures to prevent infusion-related reactions will include medication with dexamethasone, acetaminophen (paracetamol), and an antihistamine before each daratumumab administration.

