5. TREATMENT ALLOCATION AND BLINDING

Treatment Allocation

Eligible subjects will be stratified by International Staging System (I vs II vs III see Attachment 8), region (North America vs Other), and age (<75 vs ≥75) and then randomized to treatment in a 1:1 ratio to either Treatment Arm A (Rd alone) or Treatment Arm B (daratumumab+Rd [DRd]). The method of randomization is randomly permuted blocks. An interactive web response system (IWRS) will be used. Each subject will be assigned a unique subject number.

Blinding

As this is an open study, blinding procedures are not applicable.

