7. BIOMARKER

Biomarker studies are designed to identify markers predictive of response (or resistance) to daratumumab. Planned analyses are based on the availability of clinically valid assays and may be deferred if emerging study data show no likelihood of providing useful scientific information. Results of biomarker analyses may be presented in a separate report.

Blood samples will be drawn from all subjects in both treatment groups to better understand the mechanism of action and mechanism of resistance of daratumumab. Minimal residual disease (MRD) will be assessed from bone marrow aspirates for all subjects who achieve a CR/sCR. Molecular subtyping will be done to evaluate daratumumab response rates in high-risk multiple myeloma subpopulations.

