7.2.3. High-risk/Standard-risk Molecular Subgroup Analysis

High-risk and standard-risk molecular subgroups have been defined in Section 2.9.

To determine if daratumumab combined with Rd (DRd) will lead to improved clinical responses in high-risk molecular subgroups, the following exploratory analysis will be conducted by using the similar analysis methods specified in Sections 4.3.1.2 and 4.2.2.

- To evaluate ORR and MRD negativity rate for subjects in high-risk molecular subgroup and subjects with specific molecular subtyping such as del17p, t(14;16), t(4;14)
- To evaluate PFS and OS for subjects in high-risk molecular subgroup and subjects with specific molecular subtyping such as del17p, t(14;16), t(4;14)

If subgroup size allows, these results will also be compared with the subjects treated with DRd in the standard-risk molecular subgroup, to explore whether subjects treated with DRd in high risk molecular subgroup will have similar clinical outcome as subjects in standard risk subgroup.

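### Protocol 11.7 seeks predictive markers by correlation with outcome and leaves prognostic confounding to a possible later controlled study, with no treatment-by-marker interaction specified although this trial has a randomized Rd arm

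*Protocol*

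**What the plan says.** Protocol 11.7 states the aim: "Biomarker studies are designed to identify markers predictive of response (or resistance) to daratumumab". The method follows: "Correlation of baseline expression levels or changes in expression levels with response or time-to-event endpoints will identify responsive (or resistant) subgroups". No contrast between arms is stated. The section recognises that prognostic factors may confound the result, and its remedy is that a marker "could be verified in a prospective clinical study with a control treatment arm". Biomarker subjects are to be grouped by the dose prescribed, not by randomized arm.

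The trial itself is controlled. Protocol 3.1 says "This is a randomized, open-label, active controlled, parallel-group, multicenter study in subjects", and Protocol 5 says subjects are "then randomized to treatment in a 1:1 ratio to either Treatment Arm A (Rd alone) or Treatment Arm B". SAP 7 says "Blood samples will be drawn from all subjects in both treatment groups". Protocol 9.5 does not restrict the baseline marrow sample by arm, and SAP 7.2.1 describes baseline marrow and PBMC samples for sequencing.

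For risk groups defined in advance, the control arm is used:

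- Protocol 9.2.2 lists efficacy of DRd against Rd in high-risk molecular subgroups.
- SAP 7.2.3 evaluates ORR, MRD negativity, PFS and OS in the high-risk group and by specific aberration, with the between-arm methods of SAP 4.2.2 and 4.3.1.2.
- SAP 2.10 (Table 1) lists cytogenetic risk as an efficacy subgroup, and SAP 4.4 plans subgroup analyses and forest plots.

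SAP 7.2.3 then adds, if numbers allow, that "these results will also be compared with the subjects treated with DRd in the standard-risk molecular subgroup". The only interaction named in either document is treatment-by-time, in the PRO model of SAP 4.5.2.

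**The concern.** A predictive marker is one for which the effect of daratumumab differs by marker level. A prognostic marker shifts outcome in both arms alike. Correlating a marker with response or PFS, within one arm or in both arms pooled without an interaction term, picks up either kind. So does a comparison of high-risk with standard-risk subjects who all received DRd.

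The plan sees this problem but looks for the answer in another study, when for markers measured at baseline the randomized Rd arm can address it here. As written, a purely prognostic marker can be described as defining a daratumumab-responsive or resistant subgroup. The exploratory objective would then go unanswered, within the limits of power, although samples from both arms exist.

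**Working it through.** **The plan's own figure.** Protocol 11.2 gives 390 PFS events for 80% power at a hazard ratio of 0.75, two-sided alpha 0.05.

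- Schoenfeld: 4 × (1.960 + 0.842)² / (ln 0.75)² gives 380 events.
- Freedman: (1.960 + 0.842)² × (1.75/0.25)² gives 385 events.
- Power at 390 events: Φ(0.288 × √390 / 2 − 1.96) = Φ(0.88) = 81%.

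The figure reproduces, and nothing in the sample size is at issue.

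**Inputs not in the documents.** Marker prevalence p and prognostic strength are assumed; 50% and 15% prevalence are shown as a range. Event counts within DRd are rounded. If events split in proportion to the hazards, 390 × 0.75/1.75 = 167 and 234 × 0.75/1.75 = 100, so 170 and 100 are used.

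**Chance of flagging a purely prognostic marker by correlation within DRd.** With D events, the standard error of the marker's log hazard ratio is 1/√(D p(1−p)), so P = Φ(ln HR × √(D p(1−p)) − 1.96).

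| Events in DRd | Prevalence | HR 1.5 | HR 2.0 |
|---|---|---|---|
| 170 | 50% | Φ(2.64 − 1.96) = 75% | Φ(4.52 − 1.96) = 99% |
| 170 | 15% | Φ(1.89 − 1.96) = 47% | Φ(3.23 − 1.96) = 90% |
| 100 | 50% | Φ(2.03 − 1.96) = 53% | Φ(3.47 − 1.96) = 93% |

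Pooling both arms without an interaction term does not help. At 390 events, 50% prevalence and HR 1.5, P = Φ(0.405 × √390 / 2 − 1.96) = Φ(2.04) = 98%.

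**Interaction test on the same marker.** With no true interaction it rejects at its nominal 5%. A simulation of 4,000 trials checked this. It used 730 subjects, an Rd median PFS of 24 months, a treatment hazard ratio of 0.75 in both marker strata, 30% prevalence and a prognostic hazard ratio of 1.8, and averaged 437 events. Correlation within DRd flagged the marker in 97.6% of runs; the treatment-by-marker contrast flagged it in 5.4%.

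**Power of the interaction test.** The standard error of the log ratio of hazard ratios is √(4 / (D p(1−p))), and the ratio detectable with 80% power is exp(2.80 × SE).

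| PFS events, both arms | Prevalence | SE | Detectable ratio |
|---|---|---|---|
| 390 | 50% | 0.203 | 1.76 |
| 390 | 15% | 0.284 | 2.2 |
| 234 | 50% | 0.261 | 2.1 |
| 234 | 15% | 0.366 | 2.8 |

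At 390 events, power for a ratio of 0.75 is only 30% at 50% prevalence and 17% at 15%.

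**The case against.** The strongest reply is that much of this is already covered. The main part of SAP 7.2.3 is a between-arm analysis of the high-risk molecular group. The comparison within DRd is a conditional addition, meant to see whether the two risk groups fare alike. Cytogenetic risk is an efficacy subgroup with forest plots, and Protocol 11.7 allows for a meta-analysis with a method for heterogeneity. This stands: a reader might infer that the control arm is ignored, and the documents do not support that. It does not fill the gap, because a treatment effect within the high-risk group does not show that the effect differs from that in standard-risk subjects, and the open-ended expression markers have no stated arm contrast.

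A reader might also infer that the correlation is confined to DRd, or that prognostic markers are bound to be reported as predictive. Neither follows. Protocol 11.7 does not limit the analysis to one arm, permits whatever methods are appropriate, and itself warns of prognostic confounding. An interaction model is unspecified, not forbidden. External verification is also sound practice; the fault is in giving it as the means of removing prognostic confounding.

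Two further limits stand. Protocol 11.7 also covers changes in expression after treatment starts. These can be affected by treatment, so an interaction on them lacks the randomized interpretation. Power is also modest: the interim PFS analysis planned at 234 events became the primary one, and fewer than 730 subjects may have usable sequencing.

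**Conclusion.** The point holds for exploratory markers measured at baseline, and for the absence of any treatment-by-marker interaction. The method stated in Protocol 11.7 cannot separate predictive from prognostic markers, and the reason given for a later controlled study overlooks the randomized Rd arm.

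The illustrated false-flag rates run from about 47% to 99% at 170 events within DRd, against about 5% for an interaction test. They depend on the assumed prevalence and prognostic strength and on testing within DRd, so they show scale and do not predict what will be reported. It would be too strong to say that the data already in hand will settle which markers are predictive: only strong interactions are detectable.

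Marker discovery is exploratory and outside the testing hierarchy of SAP 4.1.1. No primary or hierarchical secondary conclusion changes.

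**What to change.** In Protocol 11.7 and SAP 7:

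- For markers measured at baseline, define predictive as a treatment-by-marker interaction fitted in both arms, using Cox models for PFS and OS and logistic models for response, accounting for the randomization strata. Label it exploratory.
- Report the DRd-versus-Rd effect with its confidence interval at each marker level, for the high-risk and standard-risk groups as well as the expression markers.
- Group subjects by randomized arm instead of by prescribed dose.
- Label within-arm correlations, the risk-group comparison within DRd, and post-baseline changes in expression as descriptive and unable to establish prediction.
- Present any later controlled study as replication.

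The cost is wording and a few extra exploratory models on samples already planned, with no new visits. Fewer markers will be declared predictive, and the text should say that a null interaction is inconclusive.

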11.8. Patient Reported Outcomes

EORTC-QLQ-C30 scores will be evaluated for all domains except "financial problems" among subjects with at least one post-baseline assessment and 50% completion of the relevant items for a domain. Descriptive analyses followed by mixed model repeated measures will be used to analyze each domain score. No adjustment for multiple comparisons will be made.

EQ-5D-5L scores will be summarized at each time point.

11.9. Safety Analyses

Adverse Events

The verbatim terms used in the eCRF by investigators to identify adverse events will be coded using the Medical Dictionary for Regulatory Activities (MedDRA). The severity assessment for an adverse event or serious adverse event should be completed using the NCI CTCAE Version 4. All reported adverse events with onset during the treatment phase (ie, treatment-emergent adverse events, and adverse events that have worsened since baseline) will be included in the analysis. For each adverse event, the percentage of subjects who experience at least 1 occurrence of the given event will be summarized by treatment arm.

Summaries, listings, datasets, or subject narratives may be provided, as appropriate, for those subjects who die, who discontinue treatment due to an adverse event, or who experience a severe or a serious adverse event.

Clinical Laboratory Tests

Laboratory data will be summarized by type of laboratory test. Reference ranges and markedly abnormal results (specified in the Statistical Analysis Plan) will be used in the summary of laboratory data. Descriptive statistics will be calculated for each laboratory analyte at baseline and for observed values and changes from baseline at each scheduled time point. Changes from baseline results will be presented in pre- versus post treatment cross-tabulations (with classes for below, within, and above normal ranges). Frequency tabulations of the abnormalities will be made. A listing of subjects with any laboratory results outside the reference ranges will be provided. A listing of subjects with any markedly abnormal laboratory results will also be provided.

Parameters with predefined NCI CTCAE toxicity grades will be summarized. Change from baseline to the worst toxicity grade experienced by the subject during the study will be provided as shift tables. Worst toxicity grade during treatment will be presented, according to NCI CTCAE (version 4). Clinically relevant changes (i.e. causing a treatment intervention and/or need for concomitant therapy) will be also recorded on the adverse event eCRF. All other lab abnormalities need not be recorded as adverse events.

Electrocardiogram (ECG)

Electrocardiogram data will be summarized and listed.

Vital Signs

Descriptive statistics of baseline temperature, pulse/heart rate, and blood pressure (systolic and diastolic) values will be summarized.

11.10. Interim Analysis

Two interim analyses are planned. The first interim analysis, with a purpose to evaluate safety, will be performed after a total of approximately 100 subjects have been treated for at least 8 weeks or discontinued the study treatment. The second interim analysis will be performed when 234 PFS events, which is 60% of the total planned events, have been accumulated. The purpose of this interim analysis is to evaluate cumulative interim safety and efficacy data. The significance level at this interim analysis to establish the superiority of DRd over Rd with regard to PFS will be determined based on the observed number of PFS events at the interim analysis, using the O'Brien-Fleming boundaries as implemented by the Lan-DeMets alpha spending method. If the experimental arm (DRd) is numerically worse than the control arm in terms of PFS (observed hazard ratio >1 favoring the control arm), then the study may be terminated for futility, with a conditional power of less than 20% under the alternative hypothesis given the observed interim data.

As the superiority of DRd over Rd alone with respect to PFS was established at the second interim analysis, the interim PFS analysis will serve as the primary PFS analysis, which otherwise was to occur when approximately 390 PFS events had been observed. The first interim OS analysis was performed at the interim PFS analysis. The second interim OS analysis will now occur when approximately 260 deaths have occurred which will be about the same time the primary PFS analysis would have taken place. All applicable available data prior to that time will be included in each of the respective analyses.

11.11. Data Monitoring Committee

An IDMC, consisting of 2 clinicians and 1 statistician who are independent experts not otherwise participating in the study, will be established to review efficacy and safety results at the planned interim analyses. After the interim review, they will make recommendations regarding the continuation of the study. In addition, the IDMC may also review cumulative safety data every 6 months besides the 2 interim analyses. The IDMC will no longer review study data after the interim PFS analysis has been completed. The details will be provided in a separate IDMC charter.

12. ADVERSE EVENT REPORTING

Timely, accurate, and complete reporting and analysis of safety information from clinical studies are crucial for the protection of subjects, investigators, and the sponsor, and are mandated by regulatory agencies worldwide. The sponsor has established Standard Operating Procedures in conformity with regulatory requirements worldwide to ensure appropriate reporting of safety

information; all clinical studies conducted by the sponsor or its affiliates will be conducted in accordance with those procedures.

12.1. Definitions

12.1.1. Adverse Event Definitions and Classifications

Adverse Event

An adverse event is any untoward medical occurrence in a clinical study subject administered a medicinal (investigational or non-investigational) product. An adverse event does not necessarily have a causal relationship with the treatment. An adverse event can therefore be any unfavorable and unintended sign (including an abnormal finding), symptom, or disease temporally associated with the use of a medicinal (investigational or non-investigational) product, whether or not related to that medicinal (investigational or non-investigational) product. (Definition per International Conference on Harmonisation [ICH])

This includes any occurrence that is new in onset or aggravated in severity or frequency from the baseline condition, or abnormal results of diagnostic procedures, including laboratory test abnormalities.

Note: The sponsor collects adverse events starting with the signing of the ICF (refer to Section 12.3.1, All Adverse Events, for time of last adverse event recording).

Serious Adverse Event

A serious adverse event based on ICH and EU Guidelines on Pharmacovigilance for Medicinal Products for Human Use is any untoward medical occurrence that at any dose:

- Results in death
- Is life-threatening (The subject was at risk of death at the time of the event. It does not refer to an event that hypothetically might have caused death if it were more severe.)
- Requires inpatient hospitalization or prolongation of existing hospitalization
- Results in persistent or significant disability/incapacity
- Is a congenital anomaly/birth defect
- Is a suspected transmission of any infectious agent via a medicinal product
- Is Medically Important*

*Medical and scientific judgment should be exercised in deciding whether expedited reporting is also appropriate in other situations, such as important medical events including any second primary malignancy that may not be immediately life threatening or result in death or hospitalization but may jeopardize the subject or may require intervention to prevent one of the other outcomes listed in the definition above. These should usually be considered serious.

Suspected Unexpected Serious Adverse Reactions (SUSARs)

If a serious and unexpected adverse event occurs for which there is evidence suggesting a causal relationship between the study treatment and the event (eg, death from anaphylaxis), the event must be reported as a serious and unexpected suspected adverse reaction even if it is a component of the study endpoint (eg, all-cause mortality). Refer to Section 12.3.3 for SUSAR Reporting Requirements.

Unlisted (Unexpected) Adverse Event/Reference Safety Information

An adverse event is considered unlisted if the nature or severity is not consistent with the applicable product reference safety information. For daratumumab, the expectedness of an adverse event will be determined by whether or not it is listed within the Reference Safety Information included in the Investigator's Brochure.

Adverse Event Associated With the Use of the Drug

An adverse event is considered associated with the use of the drug if the attribution is possible, probable, or very likely by the definitions listed in Section 12.1.2.

